## **5.2. *Modified Total Vaccinated cohort – (LTFU and Control group)***

The mTVC will be the primary population for efficacy analysis, which excludes subjects in the TVC for efficacy analysis who were not administered with the second vaccination during the ZOSTER-006/022 study, or who developed a confirmed case of HZ prior to 1 month after the second vaccination in the ZOSTER-006/022 primary study.

## **5.3. *According to Protocol Cohort for efficacy – (LTFU and Control groups)***

The According to Protocol (ATP) cohort for efficacy will include all evaluable subjects:

- Who meet all eligibility criteria;
- Who have received 2 doses of the HZ/su study vaccine according to their random assignment in the primary ZOSTER-006/022 studies;
- For whom administration site of study vaccine is known and correct from ZOSTER-006/022;
- Who have not received a vaccine not specified or forbidden in the protocol;
- Complying with the procedures defined in the protocol;
- Who did not receive a medication/ product leading to elimination from the ATP analysis;
- Who did not present with an IMC leading to exclusion from an ATP analysis;
- Who complied with the vaccination schedule, i.e., 49-83 days between the first and the second dose in ZOSTER-006/022;
- Who did not develop a confirmed case of HZ prior to 1 month (30 days) after the second vaccination, during the ZOSTER-006/022 studies.

#### **5.4. According to Protocol Cohort for immunogenicity – (1-Additional Dose, Revaccination and Control groups)**

The ATP cohort for immunogenicity will include all subjects from the TVC:

- Who meet all eligibility criteria;
- Who have received 1 dose (1-Additional Dose group) or 2 doses (Revaccination group) of study vaccine(s) according to their random assignment;
- For whom administration site of study vaccine is known and correct;
- Who have not received a vaccine not specified or forbidden in the protocol;
- Who complied with the procedures defined in the protocol;
- Who did not receive a medication/ product leading to exclusion from an ATP analysis;
- Who did not present with an IMC leading to exclusion from an ATP analysis;
- Who complied with the vaccination schedule, i.e., 49-83 days between the first and the second dose for the Revaccination group;
- Who complied with the Month 1 blood sample schedule, i.e., 28-48 days from Month 0 to Month 1 for the 1-Additional Dose group and Control group;
- Who complied with the post-Dose 2 blood sample schedule, i.e., 28-48 days post-Dose 2 for the Revaccination group;
- Who had immunogenicity results available post-dose 1 for the 1-Additional Dose group, post dose 2 for the Revaccination group and at Month 1 and Month 3 for the Control group;
- Who had no episode of HZ prior to study start;
- Who received 2 doses of HZ/su vaccine in the primary ZOSTER-006/022 studies.

*Please note – To avoid long title for the OPS based on this cohort, the cohort name to be used in the OPS is ‘ATP cohort for humoral immunogenicity – Randomized groups’ and ATP cohort for CMI immunogenicity – Randomized groups’ for humoral and CMI analysis, respectively.*

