**CONFIDENTIAL**

201190 (ZOSTER-049 EXT:006-022)  
Protocol Amendment 5 Final

- Who complied with the post-Dose 2 blood sample schedule, *i.e.*, 28-48 days post-Dose 2 for the Revaccination group;
- Who had immunogenicity results available post-dose 1 for the 1-Additional Dose group, ,post dose 2 for the Revaccination group and at Month 1 and Month 3 for the Control group;
- Who had no episode of HZ prior to study start;
- Who received 2 doses of HZ/su vaccine in the primary ZOSTER-006/022 studies.

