- To assess persistence of vaccine induced cell-mediated immune responses at Year 5, 6, 7, 8, 9 and 10 and beyond after the primary vaccination in the ZOSTER-006/022 studies **in the CMI subset** in subjects  $\geq 50$  YOA overall and within each of the specified age ranges\* at the time of first vaccination, in the ZOSTER-006 study;
- To assess humoral immune responses at Year 5, 6, 7, 8, 9 and 10 and beyond after the primary vaccination in the ZOSTER-006/022 studies in subjects  $\geq 50$  YOA at the time of first vaccination, in the ZOSTER-006/022 studies, who had a confirmed HZ episode previously for the timepoint considered;
- To assess vaccine induced cell-mediated immune responses at Year 5, 6, 7, 8, 9 and 10 and beyond after the primary vaccination in the ZOSTER-006/022 studies **in the CMI subset** in subjects  $\geq 50$  YOA at the time of first vaccination, in the ZOSTER-006 study, who had a confirmed HZ episode previously for the timepoint considered;
- To assess humoral immune responses one month after the first additional HZ/su vaccine dose (1-Additional Dose and Revaccination groups) and at the same timepoint in the Control group;
- To assess vaccine induced cell-mediated immune responses one month after the first additional HZ/su vaccine dose (1-Additional Dose and Revaccination groups) and at the same timepoint in the Control group;
- To assess humoral immune responses one month after the second additional HZ/su vaccine doses (Revaccination group and at the same timepoint in the Control group);
- To assess vaccine induced cell-mediated immune responses one month after the second additional HZ/su vaccine doses (Revaccination group and at the same timepoint in the Control group);
- To assess persistence of humoral immune responses at Year 1, 2, 3, 4, 5 and 6 timepoints of this study in subjects from the 1-Additional Dose, Revaccination and Control groups;

- To assess persistence of vaccine induced cell-mediated immune responses at Year 1, 2, 3, 4, 5 and 6 timepoints of this study in subjects from the 1-Additional Dose, Revaccination and Control groups;
- To assess vaccine safety and reactogenicity in the 1-Additional Dose and Revaccination groups;
- To assess vaccine safety in the LTFU and Control groups.

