### **6.3. Analysis of immunogenicity**

The primary immunogenicity analysis will be based on the ATP cohort. If, in any vaccine group the percentage of vaccinated subjects with serological results excluded from the ATP cohort for analysis of immunogenicity is 5% or more, a second analysis based on the TVC will be performed to complement the ATP analysis.

All analyses will be presented overall and by age strata. The main age strata for reporting purposes are 50-59, 60-69 and  $\geq 70$  YOA. Additional analysis will be presented in  $\geq 60$  YOA.

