## 11. APPENDIX 1: ELIMINATION TYPE FOR THE STUDY

*The following is the detail of the elimination type applicable for the study:-*

Eli_type	Description of eli_type
F0	Persistence analysis at M0 LTFU
F1	Persistence year 1 (Month 12) after start of Zoster 049 (Month 0) LTFU group
F2	Persistence year 2 (Month 24) after start of Zoster 049 (Month 0) LTFU group
F3	Persistence year 3 (Month 36) after start of Zoster 049 (Month 0) LTFU group
F4	Persistence year 4 (Month 48) after start of Zoster 049 (Month 0) LTFU group
F5	Persistence year 5 (Month 60) after start of Zoster 049 (Month 0) LTFU group
F6	Persistence year 6 (Month 72) after start of Zoster 049 (Month 0) LTFU group
T1	Persistence year 4 after dose 2 vaccination in Zoster 006/022 LTFU group
T2	Persistence year 5 after dose 2 vaccination in Zoster 006/022 LTFU group
T3	Persistence year 6 after dose 2 vaccination in Zoster 006/022 LTFU group
T4	Persistence year 7 after dose 2 vaccination in Zoster 006/022 LTFU group
T5	Persistence year 8 after dose 2 vaccination in Zoster 006/022 LTFU group
T6	Persistence year 9 after dose 2 vaccination in Zoster 006/022 LTFU group
T7	Persistence year 10 after dose 2 vaccination in Zoster 006/022 LTFU group

Eli_type	Description of eli_type
T8	Persistence year 11 after dose 2 vaccination in Zoster 006/022 LTFU group
T9	Persistence year 12 after dose 2 vaccination in Zoster 006/022 LTFU group
M3	Immunogenicity analysis at Month 3 for the randomized group
E2	Efficacy analysis – Interim year 2 - LTFU and Control group
E4	Efficacy analysis – Interim year 4 – LTFU and Control group
EF	Efficacy analysis – Final – LTFU and Control group
L1	Persistence year 1 Revaccination, 1-additionnal dose and control group
L2	Persistence year 2 Revaccination, 1-additionnal dose and control group
L3	Persistence year 3 Revaccination, 1-additionnal dose and control group
L4	Persistence year 4 Revaccination, 1-additionnal dose and control group
L5	Persistence year 5 Revaccination, 1-additionnal dose and control group
L6	Persistence year 6 Revaccination, 1-additionnal dose and control group

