2050*	
Underlying medical condition forbidden by the protocol
 
Time frame: - Up to Month 1 visit for 1-Additional group and Up to Month 3 for Revaccination and Control group
	M3
2060*	
Concomitant infection related to the vaccine which may influence immune response
 
Time frame: - Up to Month 1 visit for 1-Additional group and Up to Month 3 for Revaccination and Control group
	M3
2070*	
Concomitant infection not related to the vaccine which may influence immune response (e.g. Hepatitis infection in a lyme study)
 
Time frame: - Up to Month 1 visit for 1-Additional group and Up to Month 3 for Revaccination and Control group
	M3
2080	
Vaccination done but: non-compliance with vaccination schedules (dates of vaccination not corresponding to protocol intervals or unknown vaccination dates)
 
Comment – Revaccination group – VAC1- VAC2 = 49-83 days
	M3

Elimcode	Description	Eli_Type
2090	Blood sample taken but: non-compliance with blood sampling schedules (dates of BS not corresponding to adapted protocol intervals or unknown BS/vaccination dates) Comment – 1. Additional dose – VAC1 – SER2 = 28-48 days; Control – VIS1 – SER2 = 28-48 days; Revaccination – VAC2 – SER 3 = 28-48 days	M3
2100	Serological results not available for antigens POST vaccination (including lost samples, blood sample not done, unable to test, absence of parallelism) during Zoster-049 study Comment – Elimination code if ALL (anti-gE and CD4/2+J frequencies) are missing at 1 month post 1 dose in 1-Additional group and post 2 doses in Revaccination group and Month 3 for Control group.	M3
2500	Other, specify: Subjects not received two doses (applicable for the Revaccination group only)	M3

\*based on CSL review of the listing

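### Month 1 immunogenicity in the Revaccination group rests on an ATP cohort selected by events after the Month 1 sample and not held to the Month 1 window

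*SAP*

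**What the plan says.** SAP 3.2 sets a secondary objective at Month 1: "To assess humoral immune responses one month after the first additional HZ/su vaccine dose (1-Additional Dose and Revaccination groups"), with Control at the same timepoint. A parallel objective covers cell-mediated immunity. SAP 6.3 fixes the main analysis set: "The primary immunogenicity analysis will be based on the ATP cohort".

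SAP 5.4 defines one such cohort for the three randomised groups, and Protocol 11.5.4 has the same rules. Its conditions include:
- "Who have received 1 dose (1-Additional Dose group) or 2 doses (Revaccination group) of study vaccine(s) according to their random assignment";
- a dosing interval of "49-83 days between the first and the second dose for the Revaccination group";
- a Month 1 sampling window of "28-48 days from Month 0 to Month 1 for the 1-Additional Dose group and Control group";
- for Revaccination, a sampling window of 28-48 days counted from dose 2. Protocol 11.5.4 introduces this condition with "Who complied with the post-Dose 2 blood sample schedule".

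SAP Appendix 5 turns these rules into elimination codes. Code 2500 reads "Subjects not received two doses (applicable for the Revaccination group only"). SAP 5.7 gives this cohort the single elimination type M3, described in Appendix 1 as "Immunogenicity analysis at Month 3 for the randomized group". The next types for the randomised groups are the yearly L1 to L6. The footnote to the SAP 5.7 table says that the adapted version of this cohort is used in tables covering Months 0, 1 and 3 and the yearly visits.

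**The concern.** Up to the Month 1 sample the 1-Additional Dose and Revaccination groups have the same experience: one dose at Month 0 and blood at Month 1. A result for one month after the first dose should admit subjects from both groups by the same rules, and only by facts settled when that sample was taken.

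The plan does otherwise for Revaccination. A subject with a good Month 1 sample is removed if dose 2 is missed or mistimed, or if the post-dose-2 sample fails. A subject whose Month 1 sample was taken off schedule is kept. Missing dose 2 need not be random: Protocol 7.5 lists anaphylaxis, a vaccine-related SAE and an HZ episode among the events after dose 1 that rule it out. A one-dose response thus becomes a response among those who went on to complete the second-dose steps.

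Off-window Month 1 samples in Revaccination also enter the Month 3 over Month 1 mean geometric increase planned in SAP 6.3.1.1, which is the within-subject view of what dose 2 adds.

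**Working it through.** **1. The rules side by side** (SAP 5.4; Appendix 5; Protocol Tables 9 and 10)

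| Rule in the M3 cohort | 1-Additional Dose | Revaccination | Control |
|---|---|---|---|
| Month 0 to Month 1 window, 28-48 days (code 2090) | checked | not checked | checked |
| Dose 2 received (2500) | n/a | required | n/a |
| Dose interval 49-83 days (2080) | n/a | required | n/a |
| Sample 28-48 days after dose 2 (2090) | n/a | required | n/a |
| Result available (2100) | post dose 1 | post dose 2 | Month 3 in Appendix 5; Months 1 and 3 in SAP 5.4 |
| Look-back, codes 1040, 2040, 2050, 2060, 2070 | to Month 1 | to Month 3 | to Month 3 |

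Protocol Tables 9 and 10 agree. A missed Month 1 window can cost ATP eligibility in 1-Additional Dose and Control (Table 9, footnote 2) but not in Revaccination (Table 10, footnote 3). Code 2100 acts only if both the anti-gE and the CD4[2+] results are missing, so one available post-dose-2 result is enough to stay in.

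**2. Subjects traced through the rules**
- Revaccination, sample on Day 30, no dose 2: removed by 2500.
- Revaccination, sample on Day 52, dose 2 on Day 60, later steps on schedule: kept.
- 1-Additional Dose, sample on Day 52: removed by 2090.
- Forbidden vaccine after the Month 1 visit and before Month 3: removed by 1040 in Revaccination, kept in 1-Additional Dose.

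**3. Does the timepoint-adapted convention cure this?** SAP 5.6 says that each timepoint uses its corresponding cohort. SAP 5.7 and Appendix 1 list only M3 and L1 to L6 for the randomised-group ATP cohorts. With no Month 1 type, M3 is what governs Month 1.

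**4. The TVC safeguard.** SAP 6.3 adds a TVC analysis when 5% or more are excluded in any vaccine group. With 60 per group, 0.05 × 60 = 3. Two exclusions (2/60 = 3.3%) do not trigger it.

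The documents give no exclusion rate, so take an assumed probability q per Revaccination subject of exclusion at or after dose 2:

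P(2 or fewer) = Σ(j = 0 to 2) C(60, j) q^j (1 − q)^(60 − j)

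| q (assumed) | expected exclusions, 60q | P(2 or fewer) |
|---|---|---|
| 2% | 1.2 | 0.88 |
| 5% | 3.0 | 0.42 |
| 10% | 6.0 | 0.05 |

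Exclusions for other reasons, or in the other vaccinated group, also count towards the trigger. The chance of having no TVC analysis is therefore at most the last column. Failure rates are not multiplied across the dose-2 conditions, because a subject without dose 2 also lacks a dose interval and a post-dose-2 sample.

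**5. Size of the shift in the Month 1 geometric mean.** If k of 60 are excluded and their concentrations differ R-fold from those retained, full-group GMC / retained GMC = R^(k/60).

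| k | R = 2 (assumed) | R = 0.5 (assumed) |
|---|---|---|
| 2 | 2^(2/60) = 1.023 | 0.977 |
| 3 | 2^(3/60) = 1.035 | 0.966 |
| 6 | 2^(6/60) = 1.072 | 0.933 |

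The documents state no precision or power figure for this objective, so there is none to reproduce.

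**The case against.** The best defence is that this is a deliberate convention: each group is judged at its final dose, and Protocol Table 10 and SAP 5.4 agree on it. A single completer cohort also serves the Month 3 over Month 1 ratio, which needs the same subjects at both timepoints. That stands as a reason to keep M3 for Month 3 and for that ratio. It does not justify using M3 for a one-dose result at Month 1.

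The second defence is the TVC analysis. It would run in most cases where losses are material, and a Revaccination subject with one dose and a valid Month 1 sample belongs to the TVC (SAP 5.1). This limits the harm. But the TVC relaxes the ATP filters; it does not apply a common Month 1 rule to the groups, and at two exclusions or fewer it need not run.

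Third, the change comes late. The Month 3 analysis is the first step in SAP 8.1 and feeds the Year 2 report, while SAP Amendment 3 is dated September 2023. Silently replacing the cohort would look post hoc. This is a fair point, and the fix has to allow for it.

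A reader might also infer that any missing post-dose-2 result, or any pIMD, removes a Revaccination subject. The documents do not say so. Code 2100 needs all results missing, and under Protocol 7.5 a pIMD bars dose 2 only when the investigator judges the risk unacceptable.

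**Conclusion.** The point holds as a cohort-definition weakness with a probably small effect. The unequal rules are explicit in both documents and no Month 1 cohort exists to override them. Under an assumed 2-fold difference between excluded and retained subjects, the Revaccination Month 1 geometric mean moves by about 2% for 2 exclusions and 7% for 6. The exclusion counts and the 2-fold difference are assumptions. All analyses are descriptive, with no success criteria.

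A reader might go further and conclude that the filtering distorts a planned comparison of the two vaccinated groups at Month 1. The visible text does not support that: SAP 7.10.2 defines ratios of each vaccinated group over Control, and the exploratory between-group text in SAP 6.3.1.1 is redacted. A reader might also conclude that the two groups ought to be pooled at Month 1. No objective asks for a pooled estimate, and pooling is a separate preference that says nothing about the selection described here.

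**What to change.** Add a Month 1 elimination type for the randomised groups, with the same rules in all three:
- sample 28-48 days from Month 0;
- an available Month 1 result;
- look-back to the Month 1 visit for codes 1040, 2040, 2050, 2060 and 2070.

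At Month 1, do not apply 2500, 2080, the post-dose-2 part of 2090 or the post-dose-2 part of 2100 to Revaccination, and do not require a Month 3 result for Control. While editing, reconcile the Control result requirement between SAP 5.4 and code 2100.

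Keep M3 for Month 3 and for the Month 3 over Month 1 ratio. Off-window Month 1 samples will remain in that ratio, so footnote how many there are.

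Because Protocol 11.5.4 has the same rule and the Month 3 analysis comes first in the sequence, record this as a change from planned analyses and show the new Month 1 table beside the M3-based one. The cost is one extra cohort and table, and slightly different denominators at Month 1 and Month 3. A few off-window Revaccination samples leave the Month 1 set and a few valid ones return.

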#### **5.5. According to Protocol Cohort for persistence of immunogenicity – (LTFU group)**

The ATP cohort for persistence of immunogenicity (humoral/CMI) for **LTFU group** will include all evaluable subjects, i.e., those who were included in the ATP cohort for immunogenicity (humoral/CMI) in the primary ZOSTER-006/022 studies, or were excluded from this cohort solely because they had no blood samples taken, or because of incompliance with blood sample schedule, and:

- Who did not receive a concomitant medication/product leading to elimination from the ATP analysis for immunogenicity up to the timepoint considered (*section 7.6.2 of the protocol*)
- Who did not present with an IMC leading to elimination from the ATP analysis for immunogenicity (including HZ infection) up to the timepoint considered (*section 7.7 of the protocol*)
- For whom persistence immunogenicity results are available for the considered time point in ZOSTER-049 study.

*Please note – “ATP cohort for humoral persistence – LTFU” and “ATP cohort for CMI persistence - LTFU” are used in OPS to differentiate humoral and CMI results and avoid long titles for tables based on this cohort.*

## **5.6. According to Protocol Cohort for persistence of immunogenicity – (1-Additional Dose, Revaccination and Control groups)**

The ATP cohort for persistence of immunogenicity will include all evaluable subjects i.e., those who were included in the ATP cohort for immunogenicity – *Randomized group* in the ZOSTER-049 study, or were excluded from this cohort solely because they had no blood samples taken or because of incompliance with blood sample schedule, and:

- Who did not receive a concomitant medication/product leading to elimination from the ATP analysis for immunogenicity up to the timepoint considered (*section 7.6.2 of the protocol*)
- Who did not present with an IMC leading to elimination from the ATP analysis for immunogenicity (including HZ infection) up to the timepoint considered (*section 7.7 of the protocol*)
- For whom persistence immunogenicity results are available for the timepoint considered.

*Please note – To avoid long title for the OPS based on this cohort, the cohort name to be used in the OPS is ‘ATP cohort for immunogenicity persistence – Randomized groups’.*

*For the immunogenicity/persistence tables where different timepoints are presented, the concept of “Adapted ATP/TVC cohort” will be used to denote that for each timepoint, the corresponding ATP/TVC cohort for immunogenicity has been used.*

## 5.7. Elimination from study cohorts

*The elimination code and elimination type applicable for cohorts are mentioned below:*

Cohort	Elimination codes	Eli Type
TVC – Randomized groups	900, 1030	M3
TVC for humoral persistence – LTFU	900, 2130, 3615, 3616, 2110	F0 - F6 T1 - T9
TVC for CMI persistence – LTFU	900, 2130, 3615, 4130, 2111	F0 - F6 T1 - T9
TVC for immunogenicity persistence – Randomized groups	900, 1030	L1 - L6
HZ subset for HI	900, 901, 2110 for HI	HS1-HS6
HZ subset for CMI	900, 901, 2111 for CMI	HS1-HS6
TVC Efficacy – LTFU and Control group	900, 901	EF
mTVC – LTFU and Control group	900, 901, 1071, 1501, 2501, 3501	E2, E4, EF
ATP cohort for efficacy - LTFU and Control group	900, 901, 1040, 1041, 1051, 1061, 1071, 1081, 1091, 1501, 1600, 1601, 2040, 2041, 2050, 2051, 2070, 2071, 2081, 2501, 3501	EF
ATP cohort for immunogenicity - Randomized groups*	900, 1030, 1040, 1050, 1070, 1080, 1090, 1600, 2040, 2050, 2060, 2070, 2080, 2090, 2100, 2500	M3
ATP cohort for immunogenicity persistence - Randomized groups*	900, 1030, 1040, 1050, 1070, 1080, 1090, 1600, 2040, 2050, 2060, 2070, 2080, 2100, 2500	L1 – L6
ATP cohort for humoral persistence – LTFU	900, 901, 1040, 1041, 1051, 1061, 1071, 1081, 1091, 1501, 1600, 1601, 2040, 2041, 2050, 2051, 2060, 2061, 2070, 2071, 2081, 2100, 2130, 2501, 3615, 3616, 2110	F0 - F6 T1 - T9
ATP cohort for CMI persistence – LTFU	900, 901, 1040, 1041, 1051, 1061, 1071, 1081, 1091, 1501, 1600, 1601, 2040, 2041, 2050, 2051, 2060, 2061, 2070, 2071, 2081, 2100, 2130, 2501, 3615, 3616, 4130, 2111	F0 - F6 T1 - T9

\*In OPS, to reduce the number of tables, “Adapted ATP cohort for immunogenicity - Randomized groups” is used in tables that include both immunogenicity and persistence of immunogenicity results, i.e., Month 0, 1, 3 and each year follow-up in ZOSTER-049.

*The specification of each elimination code is presented in the Sections [11, 12, 13, 14, 15, and 16](#) of the SAP.*

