## 12. APPENDIX 2: ELIMINATION DETAIL FOR MODIFIED TOTAL VACCINATED COHORT

Following is the elimination code applicable for modified Total Vaccinated Cohort for LTFU and Control groups:-

Elimcode	Description	Eli_Type
901	Subjects excluded from all stat analyses (please comment here below) Subjects receiving a code 901 should not receive any other elimination codes. Comment – Subjects who received code 900 in ZOSTER-006/022 studies	EF
900	Subjects excluded from all stat analyses (please comment here below) Subjects receiving a code 900 should not receive any other elimination codes. Comment - During the duration of ZOSTER 049 only	EF

Elimcode	Description	Eli Type
1071	
 
Incomplete vaccination course before treatment withdrawal
 
site or route of study vaccine administration wrong or unknown.
 
Administration not according to protocol for reason specified by the investigator, other than side, site and route.
 
Wrong side is allowed.
 
 
Comment – Subjects assigned code 1070 in ZOSTER-006/022 studies
	EF
1501	
Other, specify: Wrong replacement or study vaccine administered (not compatible with the vaccine regimen associated to the treatment number).
 
Comment – Subjects assigned 1500 in ZOSTER 006/022 studies
	EF
2501	
Other, specify: Subjects not received two doses
 
Comment – Subjects assigned 2500 in ZOSTER 006/022 studies
	EF
3501	
Subjects having an episode of HZ prior than 30 days after the dose 2 in Zoster 006/022
 
Comment – Subjects assigned 3500 in ZOSTER- 006/022 studies
	EF

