#### 14. APPENDIX 4: ELIMINATION DETAIL FOR ATP COHORT FOR HUMORAL/CMI PERSISTENCE – LTFU GROUP

Following is the elimination code applicable for ATP cohort for humoral/CMI persistence for LTFU group:

Elimcode	Description	Eli_Type
901	Subjects excluded from all stat analyses (please comment here below) Subjects receiving a code 901 should not receive any other elimination codes. Comment – Subjects who received code 900 in ZOSTER-006/022 studies	Apply to all F0 – F6, T1-T9
900	Subjects excluded from all stat analyses (please comment here below) Subjects receiving a code 900 should not receive any other elimination codes Comment - During the duration of ZOSTER 049 only	Apply to all F0 – F6, T1-T9
1041	Administration of concomitant vaccine(s) forbidden in the protocol (see also eligibility criteria) Comment – Subjects assigned code 1040 in ZOSTER 006/022 studies	Apply to all F0 – F6, T1-T9
1040*	Administration of concomitant vaccine(s) forbidden in the protocol (see also eligibility criteria) during Zoster 049 study - Including any zoster vaccine Comment - During the duration of ZOSTER 049 only	Apply to associated visit, and subsequent visit
1051	Randomisation failure (subject not randomized in the correct group) Comment – Subjects assigned 1050 in ZOSTER 006/022 studies	Apply to all F0 – F6, T1-T9
1061	Randomisation code broken at the investigator site OR at GSK Safety department Comment – Subjects assigned 1060 in ZOSTER 006/022 studies	Apply to all F0 – F6, T1-T9

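### SAP 5.7 leaves code 901 (parent-trial exclusion from every analysis) out of the two LTFU rows for TVC persistence, contrary to the code's own definition

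*SAP*

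**What the plan says.** SAP 5.7 gives one row of elimination codes per analysis cohort. For the LTFU group, the TVC row for humoral persistence reads "900, 2130, 3615, 3616, 2110" and the TVC row for CMI persistence reads "900, 2130, 3615, 4130, 2111". Both apply to elimination types F0–F6 and T1–T9.

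Code 901 is described in SAP Appendices 2, 3 and 4. The description begins "Subjects excluded from all stat analyses (please comment here below", and the comment identifies the subjects as "Subjects who received code 900 in ZOSTER-006/022 studies". Appendix 4 applies the code to all of F0–F6 and T1–T9, but its heading confines it to the ATP persistence cohorts. The same appendices limit code 900 to events during ZOSTER-049 and say that a subject with 901 should carry no other elimination code.

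Other rows of the same table do list 901. The HZ subset for humoral immunity has "900, 901, 2110 for HI" and the mTVC has "900, 901, 1071, 1501, 2501, 3501".

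SAP 6.3 makes the ATP cohort primary for immunogenicity. It adds that, where at least 5% of subjects with results in any vaccine group fall outside the ATP cohort, "a second analysis based on the TVC will be performed to complement the ATP analysis".

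**The concern.** A code that means exclusion from every analysis should appear in every cohort that could contain its carriers. Here it is missing from two. The table is the operative rule for programming, so a programmer who works from the row and not from the code's description will keep these subjects.

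What is at stake is the reading of a complementary analysis. The TVC tables are there to show whether the ATP persistence results depend on ATP exclusions. If they also contain subjects whom the parent trials ruled out of all analyses, an ATP–TVC difference no longer has a single explanation. For these subjects the parent-trial pre-vaccination value, where one exists, would also be the baseline for MGI and vaccine response (SAP 6.3.3.1) and for CMI vaccine response (SAP 6.3.3.2).

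**Working it through.** No sample size, power or error rate is involved. The check compares the 13 code lists in SAP 5.7 and reads them against the definitions in Appendices 2 to 6.

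**Step 1. Which rows list 901?**

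| Cohort row in SAP 5.7 | Subjects covered | 901 listed |
|---|---|---|
| TVC | Randomised groups | No |
| TVC, humoral persistence | LTFU | **No** |
| TVC, CMI persistence | LTFU | **No** |
| TVC, immunogenicity persistence | Randomised groups | No |
| HZ subset, HI | Includes LTFU | Yes |
| HZ subset, CMI | Includes LTFU | Yes |
| TVC Efficacy | LTFU and Control | Yes |
| mTVC | LTFU and Control | Yes |
| ATP efficacy | LTFU and Control | Yes |
| ATP immunogenicity | Randomised groups | No |
| ATP immunogenicity persistence | Randomised groups | No |
| ATP humoral persistence | LTFU | Yes |
| ATP CMI persistence | LTFU | Yes |

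Seven of 13 rows list 901 and six do not. Four of the six are randomised-group rows. Of the nine rows that cover LTFU subjects, 7 list it and 9 − 7 = 2 do not.

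**Step 2. Are the randomised-group omissions the same problem?** No. Appendices 5 and 6 state that elimination codes for the randomised-group ATP cohorts come from ZOSTER-049 alone. SAP section 2 also requires these subjects to have been in the parent-trial ATP efficacy cohort, which a subject excluded from all parent-trial analyses could not be. No such reason is given for the LTFU rows.

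**Step 3. Could another code in the two rows remove a 901 subject?**
- 900 concerns ZOSTER-049 events only.
- 2130 and 4130 concern membership of the immunogenicity and CMI subsets.
- 3615 and 3616 concern whether the subject was in ZOSTER-049 at the year in question.
- 2110 and 2111 concern consent problems with a sample.

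None of them depends on a parent-trial exclusion. The rule that a 901 subject carries no other code closes the remaining route.

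**Step 4. Does the text supply the exclusion elsewhere?** SAP 5.1 defines the persistence TVC by availability of data and mentions no parent-trial exclusion. It defines the efficacy TVC in the same way, yet the TVC Efficacy row still lists 901. An inclusive TVC therefore does not explain the gap. The Document History says that SAP Amendment 2 revised the elimination section to carry parent-trial eliminations forward. No appendix covers the TVC persistence cohorts.

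**Step 5. When would it matter?** Only if the complementary TVC tables are produced. At the maximum subset sizes in Protocol Table 19, 5% is 0.05 × 1729 = 86.45, so 87 subjects for HI, and 0.05 × 234 = 11.7, so 12 for CMI. These figures only illustrate the threshold, because the rule counts subjects with results and those numbers are not known.

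**Step 6. Rows after correction.** Humoral: 900, 901, 2130, 3615, 3616, 2110. CMI: 900, 901, 2130, 3615, 4130, 2111. All nine LTFU-covering rows would then list 901.

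**The case against.** The strongest reply is that nothing shows any 901 subject to be affected. Such a subject would have to have enrolled in ZOSTER-049, belonged to the HI or CMI subset, and have a result. That stands: the number is not given and may be zero. A reader might infer from the table that excluded subjects do re-enter; the documents show only that the row would not stop them.

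The trigger is also less firm than it looks. The 5% rule in SAP 6.3 refers to the ATP cohort for immunogenicity, a name that SAP 5.4 gives to the randomised groups. The explicit persistence trigger in SAP 6.3.1.2 is for those groups too, and SAP 6.3.3, on LTFU persistence, states none. That the rule extends to LTFU is inferred from its place at the head of the immunogenicity section and from the existence of LTFU TVC rows in 5.7. The inference is fair, but it remains an inference.

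A careful programmer might also drop 901 subjects on the strength of the code's description. That would give the right result, but it would depart from the row as written.

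A reader might try to size the effect from the gap between the ZOSTER-006 maximum of 7698 (Protocol Table 1) and its mTVC of 7344 (Protocol 11.4): 7698 − 7344 = 354, or 354/7698 = 4.6%. This does not work. The gap mixes every reason for being outside the mTVC, such as a missing second dose or early HZ. It covers one parent trial, and it is not specific to 901 or to the immunogenicity subsets. The documents also do not say why code 900 was assigned, so even the direction of any shift in GMC is unknown.

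**Conclusion.** The omission is real, and as written it conflicts with the definition of code 901, with the other seven LTFU-covering rows, and with the stated purpose of SAP Amendment 2. It is a minor point. It bears only on complementary, descriptive tables, and only if three conditions hold: the 5% rule applies to LTFU persistence, the threshold is met, and at least one 901 subject enrolled and has HI or CMI results.

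No effect on GMC, seropositivity or response rates can be computed from the documents. It would be wrong to read this as a flaw in the main results. Primary efficacy uses the mTVC and LTFU persistence uses the ATP cohorts; both list 901. The prediction model in SAP 7.4.3 takes results from the adapted ATP cohort. None of these changes. It would also be wrong to extend the point to the third TVC persistence row (randomised groups), where the omission fits the design.

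**What to change.** Add code 901 to the two LTFU TVC persistence rows of SAP 5.7, humoral and CMI, for F0–F6 and T1–T9, and make the same change in the cohort program. If the sponsor means to keep these subjects, the SAP should say so and give the reason.

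The cost is one code in two table rows and a matching program edit, with no new data. While the table is open, the sponsor could also check code 3616. It is absent from the TVC CMI row but present in the TVC humoral row and the ATP CMI row.
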